Our primary outcome is radiographic evidence of fracture healing at the 12-week endpoint. At 4, 8 and 12 weeks after initiating TPTD or TPTD placebo, all patients will get follow-up pelvic radiographs, although these radiographs will stop when healing occurs. If the radiologist notes cortical bridging on the monthly x-ray, or at 3 months a confirmatory limited low dose Focus CT at the fracture site(s) will be performed to assess the degree of bridging. Cortical bridging will be quantified with bridging of 3 or 4 cortices as "healing", 1 or 2 cortices as "partial healing", and 0 cortices as "minimal/no healing" by two independent radiologists and adjudication by a third. If there are multifocal fractures, cortical bridging at each site will be evaluated and an adjudicated score representing the state of healing (0 to 4) will be recorded. Secondary analysis will examine treatment group differences in the change in follow-up pelvic fracture healing scores over the repeated monthly assessments during the 3 month placebo-controlled phase.

A secondary outcome is pain and narcotic use. The numeric rating scale (NRS) will be administered by research staff that is blinded to treatment group. We will also quantify use of narcotics and other adjunct medications for pain by recording their reported use and also asking for narcotic bottles to be brought in at each visit and performing a pill count. The NRS and recording of pain medications will be done at baseline, 4, 8 and 12 week visits and at the 6, 9 and 12 month visits.

Another secondary outcome is lower extremity physical function at 3 months and again from 3-12 months. Physical performance tests will be administered by research staff that is blinded to treatment group. The lower extremity physical function tests, tests include normal walking speed over 4 meters (with or without an assistive device), repeated chair stands (stand up from a chair with their arms folded across their chest), and balance (ability to maintain balance for 10 seconds in each of 3 positions: side-by-side, semi-tandem, and tandem foot positions). In addition, the Timed Up and Go test will be completed by each subject. Each subject will also complete the survey of ADLs and the SF-36.

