The primary outcome analysis is an ITT analysis of the categorization of the level of cortical bridging seen on focus CT at 3-months. The operational definition of cortical bridging is a five-level ordinal scale from "not healed" to "healed" (cf. protocol) adjudicated by the radiologists and clinicians, with two qualifications: 1) if endpoint assessment is missing because of a drop-out or loss-to-follow subsequent to an AE or SAE, the endpoint will be coded as "not healed"; 2) if the endpoint is missing for any other reason, the endpoint will be coded as the last available coding of the focus CT assessment. The treatment difference in cortical bridging will be evaluated by a 2x5 chi-square (group x score) with a trend test (Jonckheere-Terpstra) for the ordinal

level of bridging to see whether the TPTD treated participants “trend” to have a greater proportion of higher bridging scores than the placebo group.

Secondary analysis of the treatment group differences in the change in fracture healing scores across the 3-months of the placebo-controlled phase will use a generalized estimating equation for longitudinal repeated measures assuming a Poisson distribution with observation-level weighting from a logistic regression analysis of the missingness pattern following the approach used by Fitzmaurice, Lair and Ware (2011). The outcome will be coded as described for the primary outcome ITT analysis. Missing covariate values will be filled using the fully conditional specification multiple imputation method to impute a monotonically missing data pattern: outcomes will not be imputed. Continuous covariates will use the predictive mean matching method while classification covariates will use a logistic regression method.

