**Follow-up visits:** All visits will occur at the center where the subject was recruited and would normally be seen, following the schedule of procedures listed in Table 2. Visits will occur every month for 3 months. At every visit a pelvic radiograph will be taken. If the radiologist notes cortical bridging on pelvic x-ray, then a confirmatory low dose Focus CT at the fracture site(s) will be performed to assess the degree of bridging at the

fracture site(s). If full union is noted at the superior and/or inferior pubic fracture site(s) by focus CT, as evaluated by both radiologists, then no further radiographs or CT scans are needed, although all other assessments will continue. The CT will be done at either Ramapo Radiology in Suffern or MRI in New City, NY. At 3 months the remaining patients who still have not healed will undergo a focused limited low dose CT to quantify the degree of cortical bridging at the end of the 3 months of placebo-controlled treatment. In addition, radiographic follow-up will continue during the open label extension for those patients who have not healed during the 3 month active treatment phase.

Blood samples to assess bone turnover and calcium levels will be collected as indicated. Subjects will be encouraged at each visit to consume enough calcium and vitamin D (1000 IU vitamin D and dietary calcium with supplements as needed) and TPTD/placebo compliance will be assessed.

At each monthly visit (0 to 3), subjects will complete the lower extremity physical function test, ADLs, SF-36, NRS for pain and a narcotic use survey and pill count (details below). This information will be recorded by a research nurse blinded to treatment status since TPTD and placebo will be identical in appearance. Lower extremity physical function test, ADLs, SF-36, NRS for pain and a narcotic use survey and pill count will be repeated at 6, 9 and 12 months visits to determine if starting TPTD immediately after fracture results in better long term changes in function and pain, although the extension will be open label with all offered TPTD and analyzed as a separate secondary outcome (3 to 12 month; see below).

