**Table 2: Schedule of Procedures**

Procedure	SCR	D1	4 wk	8 wk	12 wk	6 mo	9 mo	12 mo
MMSE, Informed consent	X							
Medical history, medication list and other lifestyle	X							
Physical examination, including height and weight	X							
Screening labs (25(OH)D, PTH, Cr, Ca, prior alkaline phosphatase)	X							
Pelvic radiographs (^until healing occurs-standard care)	X		X^	X^	X^			
Pelvic limited focus CT scan (* as indicated based on cortical bridging and until healing occurs)	X full		X*	X*	X*			
Bone turnover		X	X	X	X			

Calcium for safety		X	X	X	X	X	X	X
Loading dose vitamin D (50,000 IU)	X							
Calcium (total intake 1000 mg) /1000 IU vitamin D		X	X	X	X	X	X	X
Dispense TPTD 20 mcg/day or placebo (blinded for 3 months, then open label TPTD)		X	X	X	X	X	X	X
Adverse event and concomitant medications		X	X	X	X	X	X	X
Numeric Rating scale (NRS) for pain and narcotic use survey and pill count		X	X	X	X	X	X	X
Lower extremity physical function (CSPPS and TUG)		X	X	X	X	X	X	X
Self-reported questionnaires (ADL and SF-36)		X	X	X	X	X	X	X
Telephone calls will occur weekly			X	X	X			

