**Focus CT Scan (Follow-up):** After obtaining frontal and lateral topograms of the pelvis (120 kV; 10 mA), focused helical CT will be obtained from 1 cm above the superior pubic ramus to 1 cm below the inferior ischiopubic ramus without intravenous contrast (GE LightSpeed VCT). Scans will be obtained with a slice thickness of 2.5 mm with interval of 1.25 mm, keV of 120, and Auto mA with range of 100-500 and noise index of 15.17. Sagittal and coronal reformats will also be created and reviewed. The focus CT will only evaluate superior and inferior pubic fractures, since CT determination of sacral fracture healing is difficult. At any visit where some cortical bridging is noted on the x-rays, a CT is performed and cortical bridging will be quantified with bridging of 3 or 4 cortices as "healing", 1 or 2 cortices with "partial healing", and 0 cortices with "minimal/no healing". If there are multifocal fractures, cortical bridging at each site will be evaluated and an average of cortical bridging score (0 to 4) will be recorded. If full union is noted by focus CT (evaluated by both radiologists), then no further radiographs or CT scans are needed, although all other assessments will continue. At 3 months the remaining patients who still haven't healed will undergo a focused limited low dose CT to quantify the degree of cortical bridging after 3 months of treatment. Radiographs and CT scans will continue during the open extension in those who have not yet healed. CT scans will be evaluated independently by [name], who will be blinded to treatment group. If there is a discrepancy between the score for cortical bridging (1 score difference in the reading) between them, a third reader as part

of the Contract Imaging Coordinating Center role at Weill Cornell Radiology will be brought in to blindly adjudicate the discrepancy. All CT images will be de-identified and archived using IDEAL (Imaging Data Evaluation and Analytics Lab) that houses the research PACS system with individual data devoid of any PHI and only having a subject ID.

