**Statistical Plan:** There will be no interim analysis and missing outcome data will not be imputed. Statistical analysis will be performed using SAS software (Cary NC). Between group differences at baseline will be compared with t-tests or Wilcoxon rank sum tests and chi-square tests as appropriate (p-value <0.05 for significance). Randomization by the method of randomly permuted blocks will be created for gender and BP use groups. Our primary analysis is ITT analysis and our primary outcome (SA#1) is the categorization of the level of bridging seen on focus CT into the scores from 0 to 4, described above between 0 and 3 months. The difference in cortical bridging will be evaluated by a 2x5 chi-square (group x score) with a trend test (Jonckheere-Terpstra) to see whether TPTD treated "trend" to have more higher bridging scores than the placebo group. We expect 30% - 50% superiority with TPTD at 3 months. This categorical outcome will be further analyzed with generalized estimating equations (GEE) for longitudinal repeated measures assuming a Poisson distribution with weighting from logistic regression analysis of the missingness pattern. Secondary analyses of covariates, sensitivity analyses and the "per protocol" analysis will incorporate the aforementioned approach into this aim's GEE analysis. This analysis addresses the question "Do patients treated with TPTD show more rapid fracture healing than those given placebo? For SA #2, we anticipate that the difference in pain score between the TPTD and placebo groups in the proposed study will be > 30% at each monthly time point (0-3 months). We will use a between-groups linear mixed model for repeated measures (LMMrm) to estimate the primary outcome of the difference in the mean within-subject change from baseline in the two groups at the end of the placebo controlled trial (0-3 months) and again to explore change from 3 to 12 months in the open label extension. In addition, narcotic and non-narcotic pain medication use will enter the model as time-dependent covariates. This analysis addresses the two questions, "Do patients treated with TPTD show more rapid reduction in reported pain level than those not so treated? If so, when?" For SA#3, the CSPPS is the outcome. A linear mixed model for repeated measures (LMMrm) will be used with fixed effects of treatment group (TPTD vs. placebo), time (D1, 4-, 8- and 12-wk) and their interaction, the baseline level of the CSPPS and days from injury to randomization entered as covariates, and a within-subject covariance structure selected by empirical methods prior to hypothesis testing. This plan will be repeated for the "per protocol" analysis in which subjects are limited to those showing 80% or greater compliance over the 12-week trial. This statistical plan addresses the two clinical questions, "Do patients treated with TPTD recover lower limb function faster than those not so treated? If so, when?" LMMrm will be used to analyze data from 3-12 months and assess group by time interaction. We will group on prior BP exposure strata to account for possible heterogeneity in the R-side covariance structure.

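### Before week 12 a Focus CT is done only if the x-ray shows bridging, and no rule scores the other visits, so the secondary monthly GEE of healing scores would be biased

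*Combined protocol and SAP*

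**What the plan says.** **When a CT is done.** Section 4 (Follow-up visits) sets the trigger: "If the radiologist notes cortical bridging on pelvic x-ray, then a confirmatory low dose Focus CT at the fracture site(s) will be performed". Section 7 (Focus CT Scan) repeats it: "At any visit where some cortical bridging is noted on the x-rays, a CT is performed and cortical bridging will be quantified". The CT row of Table 2 carries the same condition: "Pelvic limited focus CT scan (* as indicated based on cortical bridging and until healing occurs". Week 12 differs: "At 3 months the remaining patients who still have not healed will undergo a focused limited low dose CT", whatever the x-ray shows.

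**What is analysed.** The primary outcome is the 0 to 4 bridging score on Focus CT at 3 months. The secondary analysis in the Protocol Summary compares the arms on "change in follow-up pelvic fracture healing scores over the repeated monthly assessments during the 3 month placebo-controlled phase", using a GEE, the same outcome coding as the primary analysis, and observation weights from a logistic model of missingness.

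**What happens when a score is missing.** The Protocol Summary gives two rules. First, "if endpoint assessment is missing because of a drop-out or loss-to-follow subsequent to an AE or SAE, the endpoint will be coded as" not healed. Second, "if the endpoint is missing for any other reason, the endpoint will be coded as the last available coding of the focus CT assessment". It also says outcomes are not imputed, and the Statistical Plan in Section 7 agrees: "There will be no interim analysis and missing outcome data will not be imputed".

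**What is not said.** Zero bridged cortices is a defined category, but only as a reading of a CT that was performed. No text gives a score to an x-ray without bridging. No text says that the full screening CT is scored for bridging; it serves to classify fracture type and displacement.

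**The concern.** At weeks 4 and 8 the outcome itself decides whether it is measured. Patients with bridging are scanned and scored. Patients without bridging are not scanned, and if they have no earlier Focus CT there is nothing to carry forward.

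Weighting repairs missing data only when every kind of patient has some chance of being observed. Here that chance is zero, by design, for one kind: those with no bridging on x-ray.

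The first aim in Section 2 is earlier bridging, and the Statistical Plan says the GEE answers whether healing is more rapid on TPTD. Weeks 4 and 8 hold most of that information. A drug that moves patients from no bridging to some bridging would bring low scores into the TPTD average while the matching placebo patients stay out of theirs.

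**Working it through.** **1. The plan's own figure.** The Sample Size Justification gives 100% versus 60% healed, 40 per group, 1% alpha and power above 95%. With a pooled two-sided z-test:

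z = (|p1−p2|√n − 2.576√(2p̄(1−p̄))) / √(p1(1−p1)+p2(1−p2)) = (0.4×6.325 − 2.576×0.566)/0.490 = 2.19, so power is 98.6%.

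The figure reproduces, as does 80/(1−0.2) = 100 randomized. It concerns week-12 completers, so it does not address the gap at weeks 4 and 8.

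**2. Can weighting help?** The weighted mean for an arm at a visit is Σ(R/π)Y / Σ(R/π), with R = 1 if scored and π the modelled chance of being scored.

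- If the x-ray finding is in the model, π = 0 for unbridged patients and 1/π does not exist.
- If it is left out, software returns finite weights, but every patient who receives one was scanned because bridging was seen. Those patients then stand in for the unbridged.

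**3. Size at week 8 (illustration).** From Section 3: 9% of controls and 100% of treated patients healed at week 8 in the cited non-randomized study. Assumed: healed = 4, unhealed with x-ray bridging = 2, no bridging = 0. The share q of unhealed controls with x-ray bridging is unknown and is varied from 0 to 1. Healed patients are taken as scored. The treated mean is 4.

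- Control share scored: s = 0.09 + 0.91q
- Control mean, everyone scored: m = 0.09×4 + 0.91q×2 = 0.36 + 1.82q
- Control mean, CT-scored only: m/s

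| q | s | m | m/s | Difference, CT-scored only (4 − m/s) | Difference, all scored (4 − m) | Unscored of 50 controls |
|---|---|---|---|---|---|---|
| 0 | 0.0900 | 0.360 | 4.000 | 0.000 | 3.640 | 45.50 |
| 0.25 | 0.3175 | 0.815 | 2.567 | 1.433 | 3.185 | 34.13 |
| 0.50 | 0.5450 | 1.270 | 2.330 | 1.670 | 2.730 | 22.75 |
| 0.75 | 0.7725 | 1.725 | 2.233 | 1.767 | 2.275 | 11.38 |
| 1 | 1.0000 | 2.180 | 2.180 | 1.820 | 1.820 | 0 |

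The CT-scored column is unweighted, but weights cannot rescue it. Scanned controls score 2 or 4, so any weighted control mean is at least 2 and the difference at most 2. The all-scored difference exceeds 2 whenever 0.36 + 1.82q < 2, that is for q below 1.64/1.82 = 0.90.

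**4. Direction.** Take assumed week-8 score distributions for scores 0 to 4, with placebo at 45/20/20/8/7%.

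- TPTD at 25/20/20/18/17%: the true means are 1.82 and 1.12 (difference 0.70). Among those scoring at least 1 they are 1.82/0.75 = 2.43 and 1.12/0.55 = 2.04 (difference 0.39).
- TPTD at 25/40/20/8/7%, a shift only from 0 to 1: the true means are 1.32 and 1.12. The scored means are 1.76 and 2.04, so the sign reverses.
- If the bridged share p were equal in both arms and TPTD raised scores only among the bridged, the true difference would be p times the scored one, so the scored difference would be too large.

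Shrinkage is therefore likely if TPTD produces bridging sooner, but it is not certain.

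**5. Who is affected at week 12.** Unhealed completers are all scanned. Patients whose imaging stopped at union have a CT to carry forward. Drop-outs after an adverse event are coded not healed without a scan. That leaves drop-outs for other reasons who never had a Focus CT, including one at withdrawal. They are part of the assumed 20 drop-outs among 100, and the documents do not allow a count.

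**The case against.** The best defence is that 0 is the natural reading. X-rays are taken monthly until healing, the CT is called confirmatory, and the scale has a category for no bridged cortices. An analyst might simply enter 0. That is a sensible convention, but it is not written down, and the rules that are written refer to the Focus CT coding and to no imputation.

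Two further routes to a score exist. Withdrawing patients are asked for a final x-ray and Focus CT (Section 4, Withdrawals), with no bridging condition; this depends on consent and only helps those who leave. Table 2 also lists the full screening CT in the Focus CT row, and Section 7 reports full concordance between full-field and Focus CT. A baseline 0 could be carried forward if the plan said so, but it does not, and Section 7 separates the initial CT from follow-up Focus CT.

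A reader might infer that the primary analysis loses the least-healed patients. The documents do not support that: the week-12 CT covers everyone not yet healed, and drop-outs after an adverse event already have a code. Nor do they support a claim that more placebo than TPTD patients would be lost from the primary set.

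It also stands that this bias, in its likely direction, works against TPTD in a secondary analysis. No inflation of false positives has been shown.

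**Conclusion.** The concern holds for the secondary monthly GEE. Followed literally, the rules leave unbridged week-4 and week-8 visits without a score unless an earlier Focus CT exists, and the planned weights cannot stand in for them. The comparison of healing speed would be biased, probably towards a smaller treatment difference.

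At week 8 the illustration runs from no bias (every unhealed control shows x-ray bridging) to complete loss of a 3.64-point difference (none does), with 0 to 91% of controls unscored. It rests on the cited healing rates, the assumed 4/2/0 scores and the unknown q. It is a simple comparison of means, not a run of the weighted GEE, so it should not be read as an estimate for this trial.

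For the primary week-12 test the gap is narrow: drop-outs for reasons other than an adverse event, with no Focus CT at any time. Completers all have a score.

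**What to change.** In the SAP, before unblinding:

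1. Score a visit 0 when its x-ray shows no bridging and no CT was done.
2. For drop-outs not related to an adverse event, carry forward this combined x-ray/CT score, with 0 as the default if there was no follow-up imaging.
3. Apply the missingness weights only to visits that were genuinely missed.
4. Reconcile the statements that outcomes are not imputed with the values the Protocol Summary assigns to missing endpoints.

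This needs wording only, since the x-rays are already scheduled.

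There are two downsides. An x-ray-based 0 can miss bridging that CT would show, and it mixes instruments with the week-12 CT. Patients at week 12 who have both an x-ray without bridging and a CT show how often this happens; use them for a sensitivity analysis, noting that the rate may differ at weeks 4 and 8.

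The default 0 also has a power cost. As a bound, if all 10 assumed drop-outs per arm were coded not healed, the proportions become 40/50 = 80% and 24/50 = 48%, and the formula in the working gives 78.9% at two-sided 1% alpha, against 98.6% with all of them left out. The actual cost would be smaller where drop-outs carry a positive score, and the existing adverse-event rule already incurs part of it.

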The research nurse will record the pain assessment, administer physical performance tests using standard methodology and administer all surveys as detailed below. **Pain assessment:** The research nurse will administer the NRS for pain. Using a scale from 0 (no pain) to 10 (worst pain imaginable), the subject will report how intense their pain is now and how intense it was on average last week. They will also report how much relief from pain they have achieved using treatment for pain. For this they will use a scale of 0% (no relief) to 100% (complete relief). They will also be asked about all of the pain medications they are currently taking. In addition, the nurse will ask the subject to bring any pain medications being used to each visit so that a pill count of use can be made. **Physical Performance Measures**: The **walk** is a timed walk at normal walking speed with a meter run-in before starting the timed portion and another meter at the end of the course in order to measure each subject walking at normal speed over 4 meters. Devices such as canes and walkers are allowed and their use will be recorded. The research nurse will record the use of aids and the time required to walk on the case report form. A straight backed chair will be placed against a wall and subjects will be asked to stand with their arms folded across their chest. If they can perform this task they will be asked to repeat it five times. The research nurse will record the amount of time for 5 **chair stands** to be completed on the case report form. The **balance test** measures the ability of subjects to maintain balance for 10 seconds in each of 3 positions: side-by-side, semi-tandem, and tandem foot positions. The test will be stopped if the subject cannot maintain any position for 10 seconds. The final measure for balance is the sum of the time from the three positions (range 0-30 seconds). Subjects unable to perform any of the above three tests will be assigned a 0 score. During the course of the balance test there will be two trained individuals standing in an appropriate manner to protect a patient against any falls. The research nurse will complete the case report form and follow written instructions in the detailed clinical protocol. Scores will be calculated for the CSPPS based on these tests. **Timed Up and Go Test (TUG)**: Patients will be asked to wear their regular footwear and told that they can use a walking aid if needed (this will be recorded). The test begins by having the subject Stand up from the chair, walk to the line on the floor at a normal pace, turn, walk back to the chair at a normal pace and Sit down again. The person administering the test will time the subject using a stopwatch and record the time on case report forms.

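### The plan has no rule for patients who cannot do the Timed Up and Go, so their results are lost from that analysis as if missing at random

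*Combined protocol and SAP*

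**What the plan says.** Under Specific Methodology (Physical Performance Measures), the walk and chair stands are recorded as times and balance as a sum of holding times. The inability rule follows: "Subjects unable to perform any of the above three tests will be assigned a 0 score". Shortly afterwards the text says "Scores will be calculated for the CSPPS based on these tests".

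The TUG comes next, under its own label. Its only recording instruction, apart from noting any walking aid, is "The person administering the test will time the subject using a stopwatch and record the time on case report forms". The Protocol Summary states that "the Timed Up and Go test will be completed by each subject". No value or code is given for a patient who cannot rise or walk.

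The Exclusion Criteria remove only patients who were non-ambulatory before the fracture. Screening and baseline may take place during the initial hospitalization, and baseline falls within one month of fracture. Table 2 schedules the TUG at D1, weeks 4, 8 and 12, and months 6, 9 and 12.

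The Statistical Plan opens with "There will be no interim analysis and missing outcome data will not be imputed". It names the CSPPS as the outcome of Specific Aim 3, analysed by a linear mixed model for repeated measures, and says that other outcomes are handled in a similar way as secondary analyses. The Sample Size Justification gives a power calculation for the TUG and none for the CSPPS.

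**The concern.** Inability is the worst TUG result, and here it leaves a blank. A likelihood-based mixed model is valid when a gap can be explained by the data that were observed. A gap that exists because the patient could not stand up is informative about the missing value itself.

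If teriparatide speeds recovery, more placebo patients will be unable at weeks 4 to 12, and their poor results disappear from the comparison. A patient who goes from unable to a slow completed test contributes no recorded improvement. A mean in seconds among those able also does not compare the groups as randomized.

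The TUG is not the outcome of Aim 3, but it is the only function measure with a stated power calculation, and the Background cites it as clinical evidence of functional benefit. The plan recognizes the principle elsewhere: in the Protocol Summary, a healing endpoint missing because of drop-out after an adverse event is coded at the bottom of the scale. The TUG has no counterpart.

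**Working it through.** **1. The plan's own TUG figure.** Inputs from the Sample Size Justification: week-12 means (SD) of 22.9 (7.7) for teriparatide and 54.3 (19.9) for placebo, planning SD 18, 1% alpha, 90% power, 33 per group for the treatment effect.

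- The difference is 54.3 − 22.9 = 31.4 s.
- Week 12 alone, two-sided: n = 2 × 18² × (2.576 + 1.282)² / 31.4² = 9.8, so 10 per group.
- The stated 33 is for a repeated-measures test. The week 4 and week 8 TUG means and the within-subject correlation are not given. With assumed differences of 0, 15.7 and 31.4 s at weeks 4, 8 and 12, and SD of the visit mean = 18 × √((1 + 2ρ)/3), n is 21, 27, 32 or 37 for ρ = 0.3, 0.5, 0.7 or 0.9.

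So 33 is attainable but can be neither confirmed nor refuted. This point does not dispute it.

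**2. Effect of losing unable patients at week 12.** Assumptions: times are normal, the quoted means describe all patients, unable patients would have been the slowest, and no teriparatide patient is unable. Removing the top fraction p of a normal distribution lowers its mean by SD × φ(z)/(1 − p), where z is the (1 − p) quantile.

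| Placebo unable | Fall in placebo mean (s) | Observed placebo mean (s) | Observed difference (s) | Shrinkage |
|---|---|---|---|---|
| 0% | 0 | 54.3 | 31.4 | 0% |
| 10% | 19.9 × 0.1755/0.9 = 3.9 | 50.4 | 27.5 | 12% |
| 20% | 19.9 × 0.2800/0.8 = 7.0 | 47.3 | 24.4 | 22% |
| 30% | 19.9 × 0.3477/0.7 = 9.9 | 44.4 | 21.5 | 31% |

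If 10% of teriparatide patients are also unable, their mean falls by 7.7 × 0.1755/0.9 = 1.5 s to 21.4 s. With 30% of placebo unable, the difference is then 44.4 − 21.4 = 23.0 s. The bias depends on the imbalance between arms.

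**3. Would the conclusion change?** Take the 30% against 0% case with 40 per group, hence 28 and 40 measured, and the planning SD of 18. The standard error is 18 × √(1/28 + 1/40) = 4.44 s, and 21.5/4.44 = 4.85. Power at two-sided 1% is Φ(4.85 − 2.576) = Φ(2.27), about 99%. If the true effect is as large as planned, it would still usually be detected.

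A smaller effect is more exposed. Assume a true difference of 10 s, SD 18, 40 per group and two-sided 5%. With unable rates (placebo/teriparatide) of 0/0, 10/5, 20/10 and 30/15%, and the SDs reduced by the same truncation, the measured difference is 10, 8.4, 7.2 and 6.0 s, and power is 70%, 64%, 54% and 42%.

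**4. Baseline.** The CSPPS model includes the baseline value as a covariate. If the TUG is modelled in the same way, a patient unable at D1 has no baseline value either. The covariate imputation in the Protocol Summary is described for the healing analysis, and its use here is not stated.

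**The case against.** Several arguments on the other side have force. The TUG is an additional measure and has no analysis model of its own; the missing-at-random treatment is inferred from two general sentences in the Statistical Plan. Walking aids are permitted, care includes progressive mobilization as well as bed rest, and no figure in the documents supports any rate of inability, least of all at week 12. The illustration is one-sided, the mixed model may recover part of the loss from other visits, and in that scenario the bias runs toward no difference, so it does not create a false positive. All of this stands and limits the size of the point. It does not supply the missing rule.

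A reader might also infer two stronger things. The first is that the zero runs in the wrong direction: the form holds times ("The research nurse will record the use of aids and the time required to walk on the case report form"), so a zero would be the best possible result. The documents do not support this. They assign a score of 0, not a time of 0 seconds, and the scoring sentence that follows concerns the CSPPS. Zero as the lowest score is the natural reading and agrees with balance, where zero is worst. What remains is an ambiguity: the conversion from time to score is not written out, and it is not stated whether the zero applies to one test or to the total. The protocol refers to written instructions in a detailed clinical protocol, which was not available for this review and may settle this.

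The second is that the most disabled patients drop out of the function outcome. They do not. The Aim 3 outcome is the CSPPS, and the zero rule keeps them in it at the bottom.

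**Conclusion.** The point holds for the TUG only. Read as written, the plan leaves patients who cannot do the test without a value, and by inference analyses the gap as missing at random. If inability is more common on placebo, the estimated TUG benefit is too small: illustratively by 12%, 22% or 31% of the planned 31.4 s at 10%, 20% or 30% of placebo unable and none on teriparatide. Those rates, the normal distribution and the removal of exactly the slowest patients are assumptions. A planned effect of that size would usually survive, while a smaller one might not. Inability is probably commonest at D1 and week 4, for which the documents give no TUG means. The CSPPS analysis is not affected, and the direction of its zero rule is not shown to be wrong.

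**What to change.** - Add a code to the TUG case report form for unable for physical reasons, separate from not done, and use it at every scheduled visit.
- Prespecify a TUG analysis that keeps unable patients in as the worst result. A worst-rank analysis would do. So would reciprocal time with unable set to 0: on that scale 22.9 s is 1/22.9 = 0.044 and 54.3 s is 1/54.3 = 0.018 per second, so 0 lies below every completed test. Either is acceptable.
- State how inability at D1 enters the model as a baseline value.
- Report TUG seconds among those able alongside, as descriptive, with the number unable by arm and visit.
- As a clarification only, state that the 0 for the walk, chair stands and balance is the lowest CSPPS component score and not a recorded time.

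The cost is one form code, a short addition to the statistical plan, and a less familiar scale for one analysis.
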